### *Project Objective*

Using informational emails to increase CSR Silver enrollment among unemployment recipients

### *Evaluation Design*

#### **Test Arms / Treatment Conditions:**

This is a randomized intervention where households who reported receiving unemployment insurance (UI) in 2021, had an email address and were enrolled in non-silver tier plans as of June 2021 were assigned to one of two arms: (1) a control group or (2) an informational email treatment group. Households in the treatment arm were assigned to receive two emails in June and July 2021 that encourage switching metal tiers (from Catastrophic, Bronze, Gold or Platinum to CSR Silver).

#### **Total Number of Observations:**

N = 42,470 households eligible for Cost-Sharing Reduction (CSR) Silver 94 plans but enrolled in non-silver tier plans in late-June 2021.

#### **Randomization / Assignment:**

Randomization was done at the household level. 75% of households were randomly assigned to two informational emails in late June and mid-July, respectively, and the remaining 25% were randomly assigned to no outreach during the intervention period beyond an eligibility redetermination notice.

#### **Power:**

To arrive at an estimate for the minimum detectable effect (MDE) for our primary outcome, we assume a baseline metal tier switch rate of 10 percent. The intervention was powered at the 80% level to detect a 1 percentage point increase in the CSR Silver enrollment rate.

#### **Meaningful Effect Size:**

In previous RCTs designed to induce plan switching, we have observed intent-to-treat (ITT) effects between 0.7 to 3.9 percentage points. Given the low-cost nature of this nudge (i.e. approximately \$0.02 per household), even a 1 percentage point increase in CSR Silver take-up would be meaningful.

#### **Likely Effect Size:**

Based on prior choice error nudges carried out by Covered California, we would expect to observe an ITT effect between 1-4 percentage points.

### *Data and Data Structure*

#### **Outcomes:**

The primary outcome of interest will be an indicator for whether a consumer is enrolled in a CSR Silver plan by the end of July 2021. Our secondary outcomes will include (1) an indicator for whether someone had an office visit between July 2021 and December 2021 (2) an indicator for whether someone had a prescription drug fill between July 2021 and December 2021, (3) an indicator for whether someone had

an emergency room visit between July 2021 and December 2021, (4) an indicator for whether someone had a hospital admission between July 2021 and December 2021.

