**Follow-Up Analyses**

We will examine treatment heterogeneity by self-reported race and ethnicity, baseline metal tier, age bracket and income bracket. In addition, as part of our complier average causal effect analysis, we will examine the effects of CSR Silver enrollment (among households induced to enroll in a CSR Silver plan as a result of random assignment) on our four utilization outcomes.

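### Should utilization be counted only from August in the complier analysis of CSR Silver enrollment, because households can still be switching during July?

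*SAP*

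**What the plan says.** Under Total Number of Observations, every household in the sample was "enrolled in non-silver tier plans in late-June 2021". Under Randomization / Assignment, 75% of households were assigned to "two informational emails in late June and mid-July, respectively".

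Under Outcomes, the primary outcome is whether the consumer is "enrolled in a CSR Silver plan by the end of July 2021". The four secondary outcomes (office visit, prescription fill, emergency room visit, hospital admission) are any-event indicators over July to December 2021. The first reads "an indicator for whether someone had an office visit between July 2021 and December 2021".

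Statistical Models introduces two-stage least squares for treatment receipt. Follow-Up Analyses then extends the complier work: "we will examine the effects of CSR Silver enrollment" on those four outcomes, among households that random assignment induced to enroll. The SAP gives no coverage effective date, and no rule that an event must come after the switch.

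**The concern.** Set side by side, these dates mean that CSR Silver enrollment is acquired between late June and 31 July, while the outcome window is already open from July. A household moved by the second email cannot have switched before mid-July.

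Because each outcome records any event, a single visit or fill before the switch sets the indicator to 1, and later coverage cannot alter it. That household cannot show an enrollment effect. The first stage is the same whichever outcome window is used, so any dilution of the numerator passes in full into the two-stage least squares coefficient. An analysis meant to show what CSR Silver enrollment does to use would then understate it, mostly for common outcomes. Counting events only from 1 August would seem an easy remedy.

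**Working it through.** **What is not affected.** The ITT comparison of July–December use is a randomized contrast, and the first email precedes the whole window. The primary outcome does not involve the utilization window. Only the complier analysis of enrollment is in question.

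**Inputs from the SAP.** N = 42,470 at 75:25, so 31,852.5 and 10,617.5 households; an expected enrollment effect of 1–4 percentage points (Likely Effect Size); two-sided 0.05. The plan's own power statement reproduces with this N and allocation: at a 10% baseline, the effect detectable with 80% power is 0.97 percentage points, against the stated 1.

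**Assumptions.** The SAP gives no utilization rates, no effect on use and no switch dates. Take a constant monthly hazard h, six-month control prevalence P of 20%, 50% or 70%, and a hazard ratio of 1.2 after the switch.

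**Formulas.** h = −ln(1−P)/6. For a switch acting s months after 1 July:
- July–December risk difference: d6(s) = exp(−6h) − exp(−hs − 1.2h(6−s))
- August–December risk difference: d5 = exp(−5h) − exp(−6h), since 5 × 1.2h = 6h
- z ratio = [d6/√(P(1−P))] / [d5/√(P5(1−P5))], with P5 = 1 − exp(−5h)

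**Worked case, P = 50%.** h = 0.1155 and P5 = 0.4388.
- d5 = 0.5612 − 0.5000 = 0.0612
- d6(1) = 0.5000 − exp(−7h) = 0.5000 − 0.4454 = 0.0546 (0.05455 unrounded)
- d6(0) = 0.5000 − exp(−7.2h) = 0.5000 − 0.4353 = 0.0647
- risk-difference ratio for s = 1: 0.05455/0.06123 = 0.89
- z ratio for s = 1: 0.891 × 0.4963/0.5000 = 0.88

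**July–December relative to August–December, all three prevalences**

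| Switches act from | Risk-difference ratio (20 / 50 / 70%) | z ratio (20 / 50 / 70%) |
|---|---|---|
| all 1 August | 0.96 / 0.89 / 0.82 | 0.90 / 0.88 / 0.86 |
| half 1 July, half 1 August | 1.06 / 0.97 / 0.89 | 0.99 / 0.97 / 0.94 |
| all 1 July | 1.15 / 1.06 / 0.96 | 1.08 / 1.05 / 1.01 |

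August–December has the larger z unless more than about 54% / 70% / 92% of switches act from 1 July. At 3% and 10% prevalence the risk difference shrinks by at most 0.5% and 1.7%, and at the half-and-half mix the z ratio is 1.00.

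Not all of the shortfall comes from events before the switch. At 70% with every switch acting from 1 July, no event precedes exposure, yet the risk-difference ratio is 0.96. That part arises because a common any-event indicator saturates over a longer window.

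**Absolute size.** With first stage F, expected z = F·d / [√(P(1−P)) × √(1/10,617.5 + 1/31,852.5)], where the last root is 0.01121. Take the case most favorable to a change: F = 0.04 and all switches from 1 August. At P = 50%, July–December gives 0.04 × 0.05455/(0.5000 × 0.01121) = 0.39, and August–December gives 0.04 × 0.06123/(0.4963 × 0.01121) = 0.44.

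| P | z, Jul–Dec | z, Aug–Dec | Power, Jul–Dec | Power, Aug–Dec |
|---|---|---|---|---|
| 20% | 0.26 | 0.29 | 5.8% | 6.0% |
| 50% | 0.39 | 0.44 | 6.8% | 7.3% |
| 70% | 0.42 | 0.49 | 7.1% | 7.8% |

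At F = 0.01 every z is below 0.13 and power is about 5% in both windows.

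**A larger effect.** With hazard ratio 1.5, P = 70% (h = 0.2007), F = 0.04 and all switches from 1 August:
- d6(1) = 0.3000 − exp(−8.5h) = 0.3000 − 0.1817 = 0.1183, standard error √(0.7 × 0.3) × 0.01121 = 0.00514, z = 0.04 × 0.1183/0.00514 = 0.92, power about 15%
- d5 = 0.3667 − exp(−7.5h) = 0.3667 − 0.2220 = 0.1447, standard error √(0.6333 × 0.3667) × 0.01121 = 0.00540, z = 0.04 × 0.1447/0.00540 = 1.07, power about 19%

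Both remain far from 80%.

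**The case for a change.** The best case for a change is that exposure and outcome are visibly misaligned, that a reader would naturally take the effect of enrollment to mean use after enrollment, and that the remedy is one sentence with no new data. Precision is also scarce, since the numerator is divided by 0.01–0.04. If all switches act from 1 August, making up the lost z would take 1/0.904² = 1.22, 1/0.884² = 1.28 or 1/0.860² = 1.35 times as many households at 20%, 50% and 70% prevalence.

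The misalignment stands, and so does the direction of the dilution for common outcomes with late switches. The inference to a different window does not:
- The gain reverses if switches act early in July, and the SAP has no information on this. August–December would discard July use truly caused by early switches, at a cost in z of up to about 9% (3% prevalence).
- Emergency visits and admissions, if rare, have almost no dilution to remove.
- With a different window, the complier estimate would no longer be the main July–December ITT estimate divided by the first stage, which is the link that makes it easy to read.
- Adding an August–December ITT sensitivity analysis as well would double the utilization ITT tests from four to eight, in a plan without multiplicity correction.

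**Conclusion.** No change to the plan is needed. The July–December window overlaps the month in which enrollment is acquired, and for common outcomes this can modestly dilute the enrollment estimate. As written, though, that estimate has a clear meaning: the effect of being enrolled by the end of July on use from July to December. It is the ITT effect on use divided by the ITT effect on enrollment. Follow-Up Analyses claims no particular duration of coverage, so describing the result in those terms when reporting it is enough.

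At hazard ratio 1.2, the z ratio runs from 0.86 to 1.08 across the timing and prevalence scenarios tabulated, so neither window is better throughout. In the most favorable of these cases for August–December, power moves from 7.1% to 7.8%. These figures rest on a constant hazard and on assumed prevalences, hazard ratios and switch dates. A hazard ratio of 1.5 widens the gap (about 15% against 19% at 70% prevalence with late switches) but leaves both windows badly underpowered. Analysts who want to see the sensitivity can run an August–December version for office visits and fills, noting the exposed time it loses; the plan does not depend on it.

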**Data:**

We will use Covered California administrative data to obtain enrollment outcomes and baseline demographics for our sample and Healthcare Evidence Initiative data to obtain utilization outcomes.

**Quality Control Checks:**

After carrying out the randomization, we checked for balance across several observable covariates (e.g. language spoken, self-reported race and ethnicity, baseline metal tier and income as a percent of the federal poverty level), which indicated there were no significant dissimilarities across treatment arms.

**Statistical Models & Hypothesis Tests**

This section describes the statistical models and hypothesis tests that will make up the analysis—including any follow-ups on effects in the main statistical model and any exploratory analyses that can be anticipated prior to analysis.

**Statistical Models:**

Intent-to-treat: to estimate treatment effects, our primary analysis will be an intent-to-treat (ITT) specification, examining the effect of treatment assignment. We will estimate the effect of the treatment using ordinary least squares (OLS) regression. That is, we will regress the outcome of interest (e.g. Silver enrollment) for household  $i$  on the treatment indicator:

$$outcome_i = \alpha + \beta_1 Emails_i + \epsilon_i$$

The coefficient  $\beta_1$  will be the estimate of the causal effect of the intent to treat of informational emails.

Complier average causal effect: we expect some noncompliance among those households assigned to receive emails as they may have opted out of email communications from Covered California or provided an invalid email address. Thus, to augment our ITT analysis, we will also estimate treatment effects based on treatment receipt, using two-stage least squares regression (2SLS).

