**Inference Criteria, Including Any Adjustments for Multiple Comparisons:**

We will not perform any corrections for multiple hypothesis testing, and we will use two-tailed tests with p-values  $\leq 0.05$  to denote statistically significant effects.

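### The ITT model omits baseline covariates already held; pre-specified adjustment would be a small, nearly free precision gain, not a correction of an error.

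*SAP*

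**What the plan says.** The SAP's Statistical Models section gives one ITT equation for all outcomes: "we will regress the outcome of interest (e.g. Silver enrollment) for household" on an intercept and the Emails indicator. There is no covariate term, and no adjusted analysis is specified anywhere else.

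The baseline variables are nonetheless at hand:

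- Data: administrative records will be used "to obtain enrollment outcomes and baseline demographics for our sample".
- Quality Control Checks: "we checked for balance across several observable covariates (e.g. language spoken, self-reported race and ethnicity, baseline metal tier and income" as a percentage of the poverty level.
- Follow-Up Analyses: "We will examine treatment heterogeneity by self-reported race and ethnicity, baseline metal tier, age bracket and income bracket".

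Between them these sections name five covariates: metal tier, income, age bracket, race and ethnicity, and language. Their only stated uses are the balance check and the heterogeneity analyses.

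**The concern.** In a randomized comparison, adjusting for baseline variables that predict the outcome narrows the interval around the same ITT effect. It needs no further households and, here, no further data. Leaving the covariates out does not bias the estimate or invalidate the test, so only precision is at stake.

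Two features of the trial limit the gain on the primary outcome. The outcome is binary with an assumed rate of about 10%. The sample is also fairly homogeneous: all households reported receiving unemployment insurance, and all are "households eligible for Cost-Sharing Reduction (CSR) Silver 94 plans but enrolled in non-silver tier plans in late-June 2021". The covariates probably explain little of who switches. For office visits, prescription fills, emergency visits and admissions, age and income may predict more, but the SAP gives neither rates nor explained variance.

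There is also a reason to decide now. If adjustment is added after outcomes have been seen, the choice of covariates is open to selection on the result.

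**Working it through.** **Inputs.** From the SAP: 42,470 households (Total Number of Observations); 75:25 allocation (Randomization / Assignment), so n₁ = 31,852 and n₀ = 10,618; a 10% control rate, since "we assume a baseline metal tier switch rate of 10 percent", and a 1 pp effect at 80% power (Power); two-sided 0.05 (Inference Criteria). R², the share of outcome variance explained by the covariates, is my assumption.

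**1. The plan's own figure.** Pooled variance under the null, unpooled under the alternative:

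- Pooled rate = (0.10 + 3 × 0.11)/4 = 0.1075
- SE₀ = √[0.1075 × 0.8925 × (1/10,618 + 1/31,852)] = 0.347 pp
- SE₁ = √[0.10 × 0.90/10,618 + 0.11 × 0.89/31,852] = 0.340 pp
- Power = Φ[(1 − 1.96 × 0.347)/0.340] = Φ(0.941) = 82.7%

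The minimum detectable effect (MDE) at 80% power is 0.966 pp, which rounds to the stated 1 pp. The SAP's power statement stands without adjustment.

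**2. With adjustment.** Both standard errors are multiplied by √(1 − R²). The equivalent number of extra households is 42,470 × [1/(1 − R²) − 1].

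| Assumed R² | SE multiplier | SE₁ (pp) | MDE (pp) | Power, 10% vs 11% | Equivalent extra households |
|---|---|---|---|---|---|
| 0 | 1.000 | 0.340 | 0.966 | 82.7% | – |
| 1% | 0.995 | 0.338 | 0.961 | 83.0% | 429 |
| 2% | 0.990 | 0.336 | 0.956 | 83.4% | 867 |
| 5% (optimistic) | 0.975 | 0.331 | 0.940 | 84.5% | 2,235 |
| 10% (optimistic) | 0.949 | 0.322 | 0.915 | 86.4% | 4,719 |

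**3. Which R² is plausible for the primary outcome?** For equal-sized strata with mean rate 10%, R² = variance of the stratum rates/(0.10 × 0.90):

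- 7% and 13%: 0.03²/0.09 = 1.0%
- 4%, 8%, 12% and 16%: 0.0020/0.09 = 2.2%
- 3.3% and 16.7%: 0.067²/0.09 = 5.0%
- 0.5% and 19.5%: 0.095²/0.09 = 10.0%

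The last two need very sharp separation between strata, so I take 1% to 2% as the working range for the primary outcome. A higher value is more plausible for utilization.

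**4. Form of adjustment under 3:1 allocation.** Additive adjustment can lose precision when effects differ between strata. Two constructed cases, each with two equal strata and overall rates of 10% and 11%, show the SE relative to the unadjusted one:

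| Control rates | Email rates | Additive | Interacted |
|---|---|---|---|
| 10%, 10% | 8%, 14% | 1.0009 | 0.9997 |
| 12%, 8% | 9%, 13% | 1.0016 | 0.9995 |

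Mean-centered covariates interacted with treatment avoid the loss asymptotically.

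**5. Simulation.** 200,000 replicates, 3:1 allocation, four equal strata at 4%, 8%, 12% and 16% plus a constant 1 pp effect, unpooled (robust) standard errors. Unadjusted: mean estimate 1.000 pp, power 83.4%. Interacted: mean 1.000 pp, power 84.2%. The ratio of the standard deviations is 0.989. The target is unchanged and the gain agrees with the formula: √(1 − 0.022) = 0.989.

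**The case against.** The strongest objection is that this is preference and not a defect. Regressing the outcome on a randomized indicator is valid and transparent, and the stated power is met. That is right as far as validity goes, and it is why the point is only optional. It does not show that information already held should go unused.

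The gain is also small. Choosing an unpooled variance in step 1 moves power from 82.7% to 83.7%, more than an R² of 2% does. The Likely Effect Size section expects 1 to 4 pp, and unadjusted power is already 99.1% at 1.5 pp. At 0.7 pp, the low end under Meaningful Effect Size, an R² of 2% raises power only from 53.1% to 53.9%. For utilization, at an assumed 30% event rate, even an R² of 10% moves the MDE only from 1.45 to 1.38 pp. All of this stands: no primary conclusion is likely to turn on adjustment.

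A third objection concerns the remedy. If the ITT model has interactions and the two-stage least squares (2SLS) model has main effects only, the complier estimate no longer equals the ITT effect divided by its first stage exactly, and the 2SLS loses the no-loss guarantee. This is true but minor. Under randomization, additive covariates in 2SLS are standard and consistent, and the mismatch is negligible.

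Finally, the change is safe only if the covariate list is fixed before outcomes are analysed, and the SAP does not say whether they have been examined. That condition belongs in the fix.

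**Conclusion.** The point holds as an optional improvement. The SAP fixes an unadjusted model for every outcome while holding five usable baseline covariates. The unadjusted analysis is unbiased and meets its stated power.

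On the primary outcome the expected benefit is a standard error 0.5% to 1.0% smaller and 0.3 to 0.7 points of power (83.0 − 82.7 and 83.4 − 82.7). This rests on an assumed R² of 1% to 2%, the 10% control rate, and the 75:25 split of 42,470 households. Confidence in the size is moderate because the SAP supplies no R². For utilization the gain could be larger but cannot be sized from the document.

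**What to change.** Before outcomes are analysed, make the main ITT model the outcome on Emails plus five pre-specified baseline covariates: metal tier, income bracket (% FPL), age bracket, race and ethnicity, and language.

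- Code each covariate once per household, because "Randomization was done at the household level" and the model is at that level; for example, use the primary applicant's age bracket, race and ethnicity, and language. Include a missing category.
- Mean-center the covariates, interact them with Emails, and use heteroskedasticity-robust standard errors.
- Report the unadjusted estimate alongside.
- In 2SLS, enter the same covariates as main effects in both stages, without interactions, so that no extra instruments are needed.

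The cost is a short SAP addition giving the list, categories, coding rule and missing category. No households, data or extracts are added.

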**Follow-Up Analyses**

We will examine treatment heterogeneity by self-reported race and ethnicity, baseline metal tier, age bracket and income bracket. In addition, as part of our complier average causal effect analysis, we will examine the effects of CSR Silver enrollment (among households induced to enroll in a CSR Silver plan as a result of random assignment) on our four utilization outcomes.

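### Do the follow-up 2SLS analyses of CSR Silver enrollment on utilization need weak-instrument-robust inference written into the SAP?

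*SAP*

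**What the plan says.** The section Statistical Models states that "our primary analysis will be an intent-to-treat (ITT) specification, examining the effect of treatment assignment", by OLS of each outcome on the assignment indicator. For noncompliance it adds: "to augment our ITT analysis, we will also estimate treatment effects based on treatment receipt, using two-stage least squares regression (2SLS". Follow-Up Analyses extends this complier analysis to a second exposure: "we will examine the effects of CSR Silver enrollment (among households induced to enroll in a CSR Silver plan" because of random assignment, with the four utilization indicators as outcomes.

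The only inference rule is under Inference Criteria: "we will use two-tailed tests with p-values" of at most 0.05, without multiplicity correction. That section does not say which standard error or test statistic goes with 2SLS, and it excludes none.

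The one CSR Silver variable the SAP defines is the primary outcome, "an indicator for whether a consumer is enrolled in a CSR Silver plan by the end of July 2021". On its strength, the Power section says "The intervention was powered at the 80% level to detect a 1 percentage point increase in the CSR Silver enrollment rate", and Likely Effect Size expects 1 to 4 pp.

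**The concern.** If the enrollment exposure is the end-of-July indicator, the first stage of the follow-up analysis is the primary treatment effect. A trial sized for 80% power on that effect has, at the powered effect, a first-stage F that averages just under 10, a value at which statisticians start to ask about weak instruments. The usual normal approximation for the 2SLS estimate is then poor, and its p-values and intervals lose their nominal error rates.

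At stake would be the reading of four follow-up results. A 2SLS estimate could be non-significant while the ITT effect on the same outcome is significant, only because two different standard errors were used for what is, under the exclusion restriction, the same null hypothesis. Reporting the first-stage F with Anderson-Rubin confidence sets would remove that mismatch at little cost.

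**Working it through.** **Inputs.** "N = 42,470 households eligible for Cost-Sharing Reduction (CSR) Silver 94 plans" (Total Number of Observations). "75% of households were randomly assigned to two informational emails in late June and mid-July" (Randomization / Assignment), so n1 = 31,852 and n0 = 10,618. Baseline 10% (Power). The SAP calls this a metal tier switch rate; using it as the control CSR Silver rate is an assumption. Two-sided alpha is 0.05. The SAP gives no utilization rates, so those below are assumed.

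**The plan's own figure.** The variance of the difference at 10% versus 11% is 0.11 x 0.89 / 31,852 + 0.10 x 0.90 / 10,618 = 0.00000307 + 0.00000848 = 0.00001155, so SE = 0.00340. The minimum detectable effect at 80% power is (1.960 + 0.842) x 0.00340 = 0.95 pp, or 0.966 pp with the pooled variance under the null. Both round to the stated 1 pp.

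**First-stage strength.** Noncentrality = d² / variance:
- 1 pp: 0.0001 / 0.00001155 = 8.66 (8.30 with the OLS standard error); the mean F is about one higher.
- From the power statement alone, whatever the baseline: (1.960 + 0.842)² = 7.85.
- 2 pp: 33.9. 4 pp: 130.5.

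**Size of the conventional test.** With one instrument and no true effect, t² = a² / (1 - 2ρa/f + a²/f²), where a is the ITT t-statistic, f the first-stage t-statistic and ρ the endogeneity correlation. At ρ = 0 this is 1/t² = 1/a² + 1/f², so the 2SLS statistic is always smaller than the ITT statistic. Simulation with binary enrollment and utilization (10% control rate, about 42% utilization, four assumed selection patterns) gave these rejection rates under the null:

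| First stage | Conventional 2SLS | ITT / Anderson-Rubin |
|---|---|---|
| 1 pp | about 1% to 3% | about 5% |
| 2 pp | about 3.5% to 4% | about 5% |
| 4 pp | about 4.7% to 4.8% | about 5% |

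At 1 pp the nominal 95% intervals therefore cover about 97% to 99%. The error rate exceeds 5% only for ρ above about 0.565. Utilization of 30% versus 90% between the non-Silver and Silver groups gives ρ of only about 0.37.

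**What Anderson-Rubin would add.** Its test of zero asks whether the ITT coefficient is zero, which the SAP's OLS regression of each outcome already tests. What is new is the confidence set. Solving the Anderson-Rubin quadratic shows that, when bounded, the set's half-width is at least the conventional one divided by sqrt(1 - 1.96²/F). At the mean F of about 9.7 that factor is 1/sqrt(1 - 3.84/9.7) = 1.29, and the simulated median is about 1.3. The set is unbounded whenever the first-stage |t| is below 1.96: 16% of trials at noncentrality 8.66, and 20% at exactly 80% power.

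**Precision.** At 42% utilization the ITT standard error is sqrt(0.42 x 0.58 x (1/31,852 + 1/10,618)) = 0.00553. The conventional half-width at a first stage of exactly 1 pp is about 1.96 x 0.00553 / 0.01 = 108 pp (simulated median about 113 pp). An effect on a binary outcome cannot exceed 100 pp, so the estimate is uninformative with either interval.

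**The case for a change.** The strongest case for a change is that 1 pp is no contrived scenario. It is the effect the trial was powered for, an effect the SAP calls meaningful, and the bottom of its expected range; earlier trials went down to 0.7 pp, where the noncentrality is about 4. At 1 pp under the null, the ITT test rejects and 2SLS does not in 2.6% to 3.8% of trials. Under a real effect the gap can be larger: at 5% utilization and a 30-point effect not shared by households that would enroll anyway, 23.3% versus 8.4%. The remedy costs two sentences.

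These figures stand, but they do not turn a standard choice into an error. Any power lost by the 2SLS p-value is kept by the ITT test that the SAP already plans. The gap also depends on assumptions: if those households share the effect, it is 17.0% versus 15.9%, and for a shared 50-point effect 2SLS rejects more often (38.9% versus 31.8%).

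One qualification cuts the other way. The conventional test is not conservative without exception: at about 5% to 6% utilization with extreme selection (50% versus 0.5%), it rejects about 5.8% of true nulls. That excess is slight and needs an implausible pattern.

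**Conclusion.** The concern does not hold as a fault in the SAP. The plan says nothing false or contradictory here: 2SLS with a two-tailed 0.05 rule is a standard specification for a follow-up complier analysis, and the ITT analysis that carries the conclusions is untouched. The size distortion is real at a 1 pp first stage (about 1% to 3% instead of 5%), small at 2 pp and negligible at 4 pp.

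The alternative offers no clear gain. Its test is already in the plan as the ITT regression, and its first-stage evidence is already the primary result. Its intervals exchange finite ones that cover more than 95% in the realistic scenarios for ones about 1.3 times as wide, with an unbounded set in about one trial in six at 1 pp. Competent statisticians would differ on that exchange.

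This rests on reading the enrollment exposure as the end-of-July indicator, on 10% as the control CSR Silver rate, and on assumed utilization rates and selection. At 1 pp the conventional test rejects 2.3% to 3.0% if the control rate is 5%, and 0.7% to 3.3% if it is 15%; neither changes the conclusion.

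### Does the complier analysis of utilization fail because its CSR Silver exposure carries no date?

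*SAP*

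**What the plan says.** Follow-Up Analyses adds a second instrumental-variable analysis to the plan: "we will examine the effects of CSR Silver enrollment (among households induced to enroll in a CSR Silver plan" by their random assignment), with the four utilization indicators as outcomes. It attaches no date to that enrollment.

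The other relevant places in the SAP are these:

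- **Outcomes.** The primary outcome is "an indicator for whether a consumer is enrolled in a CSR Silver plan by the end of July 2021". The utilization outcomes cover a longer period; the first is "an indicator for whether someone had an office visit between July 2021 and December 2021", and the other three use the same window.
- **Statistical Models.** The two-stage least squares analysis described there has a different exposure: "we will also estimate treatment effects based on treatment receipt". Receipt means getting the emails, so this section does not date the Silver exposure.
- **Power.** The planning rate is given as "we assume a baseline metal tier switch rate of 10 percent". The target is a 1-point rise in CSR Silver enrollment, again undated.
- **Likely Effect Size.** "we would expect to observe an ITT effect between 1-4 percentage points".
- **Data.** "We will use Covered California administrative data to obtain enrollment outcomes".

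**The concern.** The utilization window runs five months past the only dated enrollment status. A reader could therefore ask whether the exposure is status at the end of July, status in December, or any CSR Silver enrollment from July to December. These are different variables with different first stages.

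Take a household that the emails move into CSR Silver in July but that would have switched by itself in, say, October. Under the end-of-July exposure it is a complier. Under a December or ever-enrolled exposure it counts as enrolled whichever arm it is in, so it leaves the denominator. Its extra Silver months still contribute to the numerator, and the ratio is too large for the complier group it claims to describe.

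Two things would be at stake: the size and meaning of the complier estimate, and the freedom to choose the exposure date after seeing the data in a plan that tests at 0.05 without multiplicity correction.

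**Working it through.** **Inputs from the SAP.** N = 42,470; 75/25 allocation, so n1 = 31,852.5 and n0 = 10,617.5; baseline rate 10%; expected effect d of 1 to 4 points; two-sided 0.05; 80% power.

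**The plan's own figure.** With variance at the baseline rate, SE = √[0.10 × 0.90 × (1/31,852.5 + 1/10,617.5)] = 0.00336, and the minimum detectable effect is (1.96 + 0.84) × 0.00336 = 0.94 points. Letting the treated arm have its own variance gives 0.97. Both round to the stated 1 point; power at exactly 1 point is 82.7%. The planning figures are sound and can be used below.

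**Assumptions not in the SAP.** The 10% is read as controls enrolled by the end of July. After July, households not yet in CSR Silver switch in at the same monthly rate h in both arms. Nobody leaves. The effect on use is proportional to months in CSR Silver. The SAP gives no value for h, so a range is shown.

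**First stage in December.** Let s = (1 − h)^5. Then controls are at 1 − 0.90s, treated at 1 − (0.90 − d)s, and the difference is d·s. The numerator is the same intent-to-treat effect under every exposure, so the December estimate is 1/s times the end-of-July estimate. First-stage F = (difference/SE)², with SE = √[p1(1 − p1)/n1 + p0(1 − p0)/n0].

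| h per month | s | 1/s | Controls in CSR Silver, December | F, d = 1 pt | F, d = 4 pt |
|---|---|---|---|---|---|
| 0 (equals end of July) | 1.00 | 1.00 | 10% | 8.7 | 131 |
| 2% | 0.90 | 1.11 | 19% | 4.2 | 66 |
| 5% | 0.77 | 1.29 | 30% | 2.3 | 36 |
| 10% | 0.59 | 1.69 | 47% | 1.1 | 18 |

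**Departure from the December complier effect.** Per unit of d, the numerator is s + Σ(t = 1..5) h(1 − h)^(t−1)(t − 0.5)/5, which is 1, 0.951, 0.882 and 0.778. Divided by s, this is 1.00, 1.05, 1.14 and 1.32, an overstatement of 0, 5, 14 and 32%. The end-of-July estimate matches its own complier effect at every h, but that follows from giving both arms the same h.

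**Set against sampling error.** Complier SE = √[p(1 − p)(1/n1 + 1/n0)]/(d·s). At p = 0.5 the numerator is 0.56 points. For the end of July this gives 0.56/0.01 = 56 points at d = 1 point and 0.56/0.04 = 14 points at d = 4 points. At s = 0.59 they become 95 and 24. Estimate and standard error are both multiplied by 1/s, so their ratio, and hence the evidence of any effect on use, does not move.

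**Which reading the text supports.** CSR Silver enrollment is dated once, under Outcomes. Power and Statistical Models then refer to it in undated shorthand, and nobody would take those as December status. December appears only in the utilization windows; no section mentions enrollment in December, ever-enrollment or monthly status. The follow-up analysis concerns households moved into CSR Silver by assignment, which is what the primary comparison measures.

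**The case for a change.** The strongest case for a change is that the exposure variable of a pre-specified two-stage least squares analysis belongs in the SAP. This SAP defines the analysis itself and never links it to the primary-outcome indicator, and one sentence would remove any room for choice after the fact. The arithmetic above is right under its assumptions, and it is true that a later exposure would not be equivalent.

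What does not stand is that the wording leaves the readings evenly balanced. The later dates have to be brought in from outside the document, while the end-of-July date is already there. The overstatement of 5 to 32% applies only to an exposure the SAP never states, and its top end needs 10% of non-switchers to move every month, which would put about 47% of controls in CSR Silver by December. The SAP does not express its 10% as a monthly rate.

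The end-of-July indicator has limits of its own. Some July use comes before enrollment. The second email goes out in mid-July, so any switching it prompts after July would affect use without entering the exposure, and the December arm difference could then hold up or grow. That strains the exclusion assumption, and writing the date down would not cure it.

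**Conclusion.** The observation is accurate but calls for no change. Follow-Up Analyses does not restate the exposure date, and a December or ever-enrolled exposure would give a larger estimate (1.11 to 1.69 times, for an assumed common switch-in rate of 2 to 10% a month) with a weaker first stage. The SAP nevertheless contains one dated definition of CSR Silver enrollment. An analyst would use it, and it gives a definable complier effect provided assignment affects use only through that status. The gap is one of cross-referencing.

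Nothing that carries the trial's conclusions is touched: the enrollment result, the four utilization intent-to-treat results and the test of any effect on use are the same under every date. The affected estimate is a follow-up whose standard error, 14 to 56 points at 50% prevalence, dwarfs the differences between readings. A cross-reference to the primary-outcome indicator would be an editorial courtesy, and a table of enrollment by arm and month is optional reporting. Neither alters what the plan already implies.
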